5.3.1.1 Participant selection

There will be **NO EXCEPTIONS** (waivers) to eligibility requirements at the time of recruitment. Questions about eligibility criteria should be addressed PRIOR to attempting to recruit the participant.

The eligibility criteria for this trial have been carefully considered and are the standards used to ensure that only appropriate participants are entered. Participants not meeting the criteria should not be entered into the trial for their safety and to ensure that the trial results can be appropriately used to

make future treatment decisions for other people with similar diseases or conditions. It is therefore vital that exceptions are not made to these eligibility criteria.

Participants will be considered eligible for enrolment in this trial if they fulfil all the inclusion criteria and none of the exclusion criteria as defined below.

5.3.1.2 Participant Inclusion Criteria

Essential inclusion criteria for participating men (assigned male at birth) are as follows:

- a) Must be 18 years of age or over
- b) Must have a borderline or mild intellectual disability (i.e. an IQ below 80 or VCI below 80, if not possible to calculate a FSIQ) and deficits in adaptive behaviours, with or without autism. Assessments of IQ and adaptive behaviour need to have been conducted since the age of 18 years. If an assessment is dated before the 18th birthday **OR** there have been subsequent head injuries or symptoms of dementia, then a new assessment will be required. This can be conducted by a HaSB-IDD Research Assistant. Any potential participants with an IQ above 80 need to be discussed with the CI/TMG on a case-by-case basis
- c) Must have a documented history of one or more incidents of Harmful Sexual Behaviour (HSB), within the last 5 years but need not have a conviction for HSB. Any men who have not exhibited harmful sexual behaviour in the last 5 years, who are on 1:1 or similar supervision for risk management related to harmful sexual behaviour can be considered for the trial. Confirmation would need to be provided to the trial team of the nature and dates of harmful sexual behaviour that has led to the current level of supervision along with confirmation of behaviours which present as posing a risk for engagement in harmful sexual behaviour or cognitive distortions commensurate with harmful sexual behaviour.
- d) Must have relatively good verbal comprehension (to be judged by clinicians).
- e) Must have capacity to make a decision as to whether they wish to take part in trial (to be assessed during the informed consent process with a suitably qualified member of staff employed by the participating site, entered on the delegation log and having completed GCP training).

In addition, some measures will involve the participant's family carer or paid carer, depending on with whom he lives and who provides him with support. Provided the man with IDD agrees, the carer who he nominates will also be asked for their informed consent.

5.3.1.3 Participant Exclusion Criteria

Exclusion criteria for the men are:

- a) Severe mental health difficulties (chronic, debilitating, affecting cognitive functioning) that would prevent him from taking part in group CBT (as judged by clinicians)
- b) Resident in prison or in high secure services, or on probation, with a sex offender treatment order
- c) Has received cognitive behaviour therapy for HSB in the preceding three years

5.3.1.4 Eligibility Criteria for Individuals Performing the Interventions

All sites will have suitably qualified, HCPC (Health & Care Professions Council) registered clinical and/or forensic psychologists or psychiatrists, experienced in working with men with IDD, who will lead the SOTSEC-ID treatment group. Typically the treatment sessions are facilitated by two therapists, one or more male and one or more female therapists (these rotate so there is always one male and one female therapist in each session wherever possible). Apart from the lead therapist, the others may be clinical or forensic psychologists or suitably qualified nurses or challenging behaviour specialists or other allied health professionals. All those providing the intervention will have been trained in the SOTSEC-ID model. This training involves three days of lectures, discussion and role play provided by the SOTSEC-ID trainers (see 6.4.1 for more details).

5.3.1.5 Screening Procedures and Pre-recruitment Investigations

Written informed consent to enter the trial must be obtained from participants after explanation of the aims, methods, benefits and potential hazards of the trial and **BEFORE** any trial-specific procedures. Where participants do not have an assessment for IQ, adaptive behaviour (post age 18), in order to establish their eligibility to take part in the trial, these assessments will be carried out by the research team after the consent has been obtained. The assessment and recording of harmful sexual behaviour (obtained from the consenting carer), will only be collected following the consent process. Any men found not to meet the trial eligibility criteria following these assessments will be excluded from the trial.

Written informed consent will be sought from both the participant with HSB and the carer for each man. Participant information sheets for the men will be in Easy Read with pictures, and the clinicians taking consent will ensure the men understand the information, by explaining any difficult words. They will check the men understood by asking them to explain it back. This is a widely accepted practice in IDD services.

Carers will be assumed to have capacity to consent (as recommended in the Mental Capacity Act 2005), however it is important capacity is assessed during the informed consent process. Their information sheets and consent forms will be in simple language and they will be able to ask the clinicians or Research Assistants for explanations of anything about which they are unsure.

5.4 Interventions

In Arm A, participants will receive SOTSEC-ID group CBT and risk management. In Arm B, participants will receive Treatment As Usual (TAU), likely to be mainly risk management. See below for details.

5.4.1 Arm A - Intervention

The intervention we are proposing is a group CBT programme, known as SOTSEC-ID (Sex Offender Treatment Services Collaborative – Intellectual Disabilities) - see https://research.kent.ac.uk/safer-idd/harmful-sexual-behaviour/sotsec-id-programme/, which was initially developed almost 20 years ago for men with IDD and HSB, and which has been increasingly adopted in England in health services for people with IDD. This intervention is well-established, and internationally known, with over 700 facilitators trained internationally.

However, by no means all Trusts in the UK offer such treatment for men with IDD and HSB. The second edition of the SOTSEC-ID treatment manual has just been completed and will be made available to all sites offering SOTSEC-ID treatment. The manual provides a session by session guide and is over 200 pages long (see Appendix for a brief summary of the contents of treatment). All therapists will receive free training in the SOTSEC-ID intervention. This is three days long and involves both didactic and practical training, including extensive role-play.

The intervention will be delivered to groups of participants (4 to 10 men per group, any sites only able to form a group of four men should contact the Trial Managers/ CI for a discussion), by therapists who have been trained in SOTSEC-ID. It is normal practice for services to maintain men with risk management until there are sufficient numbers to start a group: in a typical area of a Community Learning Disability Team (CLDT), with a general population 220,000, 2% of the population (i.e. 4,400) should have intellectual disabilities, and of these approx. 5% of the men (i.e. around 100) will have a history of current or past sexually harmful behaviour). Commonly, CLDT areas combine to provide such treatment (e.g. two or three boroughs will collaborate).

Treatment groups will last for six months (2 sessions each of 2 hrs per week, making 100 hours of treatment). In every group, each session will have two therapists present, and often services use a pool of three or four therapists who rotate on a weekly basis, in such a way that there is always some continuity from the previous session (therapists at each session will be recorded). The therapists will be led by a qualified HCPC registered clinical or forensic psychologist with CBT training or psychiatrist and other group facilitators may also be psychologists, or challenging behaviour specialists or nurses or allied health professionals, all of whom will have been trained in SOTSEC-ID and will have had some experience of CBT.

In treatment sessions, there will always be two therapists (in case one of the men in the group needs to leave and/or be escorted away). Of these therapists, one will be male and one female facilitator whenever possible (it is not always possible to guarantee this for 100% of sessions). Therapist supervision will be provided by an experienced practitioner (a long-term member of SOTSEC-ID), monthly during the treatment (in groups, by teleconferencing).

Typically, SOTSEC-ID has been delivered at a rate of one 2 hr session of treatment per week for the men, every week for a year (100 hrs of treatment). For this trial, however, we will offer twice-weekly sessions for six months; an equivalent number of treatment hours. Men who have completed SOTSEC-ID groups in the past were consulted about this change and thought that men would prefer it (as a year of treatment is a big commitment). Moreover the faster programme delivery is likely to be more attractive for services concerned about control groups not receiving the treatment.

The SOTSEC-ID programme will thus consist of 50 sessions, each of 2 hrs in length. The sessions are arranged in six modules:

Getting started: Group purpose; group rules; 'good lives'

- Sex education
- Cognitive model (thoughts, feelings and behaviour)
- Victim empathy
- The 4-stage model of sexual offending (thinking 'not OK' sexual thoughts; making excuses, victim blaming; planning it; doing it)
- Relapse prevention and 'Keeping Safe' plans.

Following the end of the 6 modules (after the twice weekly treatment groups), men meet for one 2hr session each six weeks, with therapists, to review (in their group) how their weeks have been going and to support the men to adhere to their 'Keeping Safe' plans.

In addition to the men's sessions, there are three sessions for carers (which run in parallel with the men's sessions) and are run by one of the therapists. There is one carer's session at the start of the intervention, one at mid-way and one at the end. This allows carers to understand the plan for the men's treatment and to be able to support the men outside their sessions.

Men will also receive risk management (RM) which typically consists of environmental adjustments, designed individually for each man, to lower his risk of re-offending. Examples of the kinds of adjustments include: ensuring the participant is accompanied by staff when out in the community; reducing the likelihood of him meeting vulnerable people who could be potential victims; avoiding various settings in the community (e.g. schools, day services). For men in secure services, these restrictions can be enforced but for men who are not legally restricted they have to remain voluntary. Research assistants will collect data to provide a thorough description of the RM element for each man, including data on the extent to which the men stick to their risk management strategies (from self-report and staff/carer report).

It is important to note that all NHS Trusts and independent health settings have risk management policies that they apply for all service users with risky behaviour, whether or not they are involved in treatment trials. Both the TAU group (see below) and the intervention group will receive risk management, according to the local policies. For the intervention group these are likely to be much better informed and targeted since, as part of the intervention, the specific risky settings and/or dynamic risk factors for the men emerge, and they will inform part of their risk management plans.

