5.1.2 Site/Investigator Eligibility Criteria

Once a site has been assessed as being suitable to participate in the trial, the trial team will provide them with a copy of this protocol.

To participate in the HaSB-IDD trial, investigators and trial sites must fulfil a set of criteria that have been agreed by the HaSB-IDD Trial Management Group (TMG) and that are defined below. Pls in sites will be termed 'clinical Pls' to distinguish them from the academic Pls at University sites.

Eligibility criteria:

- A named clinician is willing and appropriate to take Clinical Principal Investigator responsibility
- Suitably trained staff are available to recruit participants and take consent, and provide the intervention (SOTSEC-ID or TAU)
- Sufficient clinical and/or forensic psychologists/psychiatrists, with at least 3 years experience in working with men with IDD, to lead the intervention (see section 6.1.2 for details)

Research assistants are available, and are permitted by the sites, to collect data from both suitable men and from their carers. Trial sites meeting eligibility criteria will be issued with the HaSB-IDD Site File and a pack of documentation needed by the Research and Development Department (R&D) of their Trust to enable the Trust to provide confirmation of capacity and capability to undertake the study.

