5.4.2 Arm B - Usual Care

Given that we propose a cluster randomised design, some sites will be randomly allocated to receive Treatment as Usual (TAU) only. In our experience, TAU may consist of medical interventions (such as anti-androgens or anti-psychotics, though these are rarely used nowadays), nurse-delivered interventions, or counselling and risk management. Typically, the latter involves environmental adjustments (for example, being asked not to go out except with staff, being asked not to walk past schools where vulnerable children might be seen, or being asked not to attend day services with vulnerable individuals, etc). These restrictions normally form part of an individualised risk management strategy. Those in the TAU groups will not

receive any individual or group CBT interventions targeting their sexual behaviour, such as victim empathy work, cognitive distortion work, relapse prevention (sex education is permitted if need be). They may receive counselling and behavioural interventions in relation to other issues (for example anger management), and associated risk management.

We will collect data to provide a thorough description of TAU within this trial, using a proforma to record treatments received and risk management details. Additional treatments provided to men in the intervention arm will also be captured using the same form. TAU data will be collected at T2, T3 and T4 for all sites.

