Self-Esteem: for the men themselves, it is important to assist them to maintain their own self-esteem, which is often very low, at the start of treatment. At times, the intervention may threaten their self-esteem, partly because it helps them understand their responsibility for their behaviour. At other points the intervention will help them build their self-esteem, by recognizing how they are progressing towards 'good lives'. It is known that self-esteem correlates with good mental health so it is important to be sure that overall self-esteem rises with treatment, rather than falls, and for this reason a well-established measure of self-esteem adapted for people with IDD and with good psychometric properties (Dagnan & Sandhu, 1999; Keeling et al, 2007) will also be used at all time points.

Harmful Sexual Behaviour Schedule: Incidences of harmful sexual behaviour that have occurred during the 5 years prior to baseline, and then between baseline and 8 months, 8 and 12 months and 12 and 24 months will be recorded at baseline, 8, 12 and 24 month follow-up time points, respectively, using information from patient and carer report, case notes, police interviews, court appearances, and court convictions. Research assistants will report such incidents to the local clinician. Clinicians/professionals working with the participants have a responsibility and duty of care to report any safeguarding concerns or crimes, including sexual abuse, to the relevant authoritative body (local Safeguarding Board), when they are made aware of these during the trial.

5.5.2.2 Heath Economic Outcome Measures:

Client Services Receipt Inventory (CSRI): Use of health, social and CJS resources used by participants will be collected from a modified CSRI completed with participants and/or their carers; this will allow the cost of service use to be estimated. The CSRI will note if responses have been informed by reference to notes/records. Information about input from the MDT team (Q6c) at all timepoints will be collected by the Trial Managers from a delegated person in the site team. This is to protect the Research Assistants from becoming unblinded.

The EuroQol quality of life measure, EQ-5D-5L, a validated quality of life measure comprising of five questions or dimensions and a visual analogue scale will be completed to evaluate changes in quality of life.

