5.6.1 Participant Assessments

Participants' assessments will normally take place in their Community Team offices or in the secure unit, if they are detained there. Occasionally they may take place in the man's place of residence (but only if staff are present). They will be told they may bring a carer if they wish (family carer or paid carer). In our experience most men will wish to do this, as they are frequently anxious about

meeting new people (in this case the research assistant). Typically the men will ask the carer to stay for a bit, while they get comfortable with the setting and RA, and then the carer is usually able to wait outside in the waiting room. In some cases it may be necessary to conduct assessments using a web-based meeting platform (for example in the event of further restrictions due to Covid-19), though this would not be routinely offered. The men can have a carer present with them if they need support to access the web-based meeting and for other support.

The assessments on time 1, 2, 3, and 4 will take between 1 and 1.5 hours. Some men will want to do these without stopping. Some will want breaks. It will made clear to them that they may have breaks if they wish. It is anticipated that, if accompanied by a carer, it will be possible to complete the carer assessments (see Table above) after seeing each man, while the man, in turn, waits in the waiting room. Assessments are anticipated to take approximately an hour, although where short breaks are required, they may take longer; they will still be completed within one day where possible.

Research Assistants are expected to comply with local safeguarding procedures and risk assessments when undertaking assessments and interviews.

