5.9.1.3 Allocation Implementation

After the instantaneous randomisation, the allocation of each site will be communicated to the trial manager, who will communicate directly with the study sites. This allocation will not be communicated to research assistants or members of the CTU who are to remain blind to site allocations.

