5.9.2 Blinding

All researchers collecting data will be blinded to treatment arm allocation. The Chief Investigator will not be blinded. The trial manager, the local site PIs and treating therapists cannot be blinded.

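### Research assistants who must stay blind, and who obtain the QACSO, are also asked to collect each man's risk-management details, an avoidable route to unblinding that the protocol closes only for one CSRI item

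*Protocol*

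**What the plan says.** Section 5.9.2 (Blinding) states: "All researchers collecting data will be blinded to treatment arm allocation". Section 5.9.1.3 adds: "This allocation will not be communicated to research assistants or members of the CTU who are to remain blind to site allocations". The trial manager, local PIs and therapists are acknowledged in 5.9.2 as impossible to blind.

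Section 5.4.1 (Arm A) gives the assistants a further task: "Research assistants will collect data to provide a thorough description of the RM element for each man". This covers adherence to the plan, with the man himself and his staff or carers as sources. The next paragraph says that both arms receive risk management under local policy, but of the plans it says: "For the intervention group these are likely to be much better informed and targeted". The reason given is that risky settings and changeable risk factors come to light during treatment and feed into the plan.

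Section 5.4.2 describes a proforma for treatments received and risk-management details, completed at T2, T3 and T4 for all sites. Its collector is given only as 'we'. On the intervention arm it says: "Additional treatments provided to men in the intervention arm will also be captured using the same form".

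Section 5.5.2.2 assigns one CSRI item, Q6c on input from the multidisciplinary team, to the trial managers, who obtain it from a delegated member of the site team. The reason is explicit: "This is to protect the Research Assistants from becoming unblinded".

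**The concern.** Blinding the people who collect outcomes is what makes this a single-blind trial, since therapists and site PIs know the allocation. The QACSO is completed in person with men who have intellectual disability, so an assessor's expectations could influence how items are explained or answers recorded. A task that asks the assessor to find out what a man's risk plan contains, and whether he keeps to it, invites him or his carer to mention the group, its review sessions or the carer sessions.

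Randomisation by site raises the stakes. A single disclosure tells the assistant the arm of every man at that site, on average 240/30 = 8 men under the target in section 5.7.

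**Working it through.** The protocol gives no unblinding rate or other figure to reproduce here, so the check is a cross-reading of the sections.

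1. **Do the assistants obtain the primary outcome?** No single sentence says so, but the sections leave no other natural reading. Section 5.1.2 says: "Research assistants are available, and are permitted by the sites, to collect data from both suitable men and from their carers". Section 5.6.1, on the assessment visits, speaks of men anxious about "meeting new people (in this case the research assistant"). Section 5.5.1 says the QACSO is done directly with the man. No separate team for risk-management data is described.

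2. **Can the risk-management data carry information about the arm?** The protocol expects so, though only as a likelihood. Section 5.4.1 expects better-targeted plans in the intervention arm and attributes this to therapy. The programme ends with a module on relapse prevention and Keeping Safe plans, followed by six-weekly group reviews supporting adherence to them. Carers in that arm are offered three sessions. The protocol does not say that these plans or sessions are items on the assistants' form. The point is that the informants are the people who took part.

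3. **Does it matter that the instruction sits under Arm A?** If the assistants did this only in Arm A, the task itself would reveal the arm. If they do it in both arms, as the wording about every man and the next paragraph suggest, the content may reveal it.

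4. **Does the protocol accept this mechanism?** Yes. Section 5.5.2.2 removes Q6c from the assistants expressly to keep them blind. Risk-management content and adherence can plausibly reveal the arm in the same way, yet they remain with the assistants.

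5. **When does the exposure occur?** Section 5.4.1 gives no date, and the schedule in section 5.6 lists no risk-management measure at any visit. The T2, T3 and T4 dates belong to the proforma in 5.4.2, which does not name the assistants. The version 1.8 entry in section 7 says the time points were clarified for site PIs so that they know when data will be requested, which suggests that sites supply that form. Exposure at 8 months, before the 12-month QACSO, is neither stated nor excluded.

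6. **Does visit order already protect the QACSO?** In part. Section 5.6.1 anticipates carer assessments after the man has been seen. It does not require this, it does not place the man's own report of adherence after his QACSO, and it cannot protect a later visit from what was learned at a previous one.

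**The case against.** The strongest reply is that the link to the 12-month outcome is inferred. The only dated form appears to come from sites, and 5.4.1 may describe collection at any time. That stands. A reader might infer that the arm is revealed at 8 months and the blind lost before the primary assessment; the protocol does not show this.

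Second, a difference between arms is only expected. The examples in 5.4.1 and 5.4.2 are nearly the same (escorts, avoiding schools and day services), and an assistant hearing them could not readily tell the arms apart. This also stands and limits the strength of the point. It does not remove it, because the protocol itself expects therapy to shape the plans.

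Third, a man attending 50 sessions, or his carer, may disclose the arm whoever collects these data. That is true, and the change below would not close that route. It is no reason to keep an additional route that can be closed cheaply.

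Fourth, safeguards exist: allocation is withheld from the assistants, Q6c has been moved, and the version 1.8 entry in section 7 keeps assistants out of the management group. A reader might conclude that the blinding is nominal; with these safeguards in place, the documents do not support that.

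**Conclusion.** The point holds in a limited form. As written, the protocol asks people who must stay blind, and who obtain the primary outcome, to collect information that it expects to be shaped by allocation. It guards against the same mechanism for Q6c only. Sections 5.4.1, 5.4.2, 5.5.2.2, 5.9.1.3 and 5.9.2 should be reconciled.

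The conclusion rests on two readings: that the assistants named in 5.4.1 are those who do the QACSO, and that talking about risk plans can disclose therapy. Both are well supported, but the second is a likelihood. Exposure before month 12 is possible, not established. No size of bias is given, because both the share of assessments unblinded and the resulting shift in QACSO would have to be assumed, and the protocol offers a basis for neither. This is a low-cost improvement that should be made, not evidence that the primary comparison is biased. Any analysis of suspected unblinding can be left to the SAP.

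**What to change.** - **Sections 5.4.1 and 5.4.2:** name the trial managers, who are already unblinded, as collectors of risk-management and TAU/additional-treatment data for both arms, obtained from a delegated member of site staff as for Q6c. State the time points.
- **Adherence reports from the man or carer that must stay with the assistants:** collect them only after the QACSO and the other man-completed scales at that visit, preferably by someone who will not do that man's later outcome assessments.
- **Section 5.6.1:** make the order a requirement rather than an expectation, with man-completed scales first and carer and service-use data afterwards.

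The cost is a wording amendment, modest extra work for the trial managers, and possibly less detail on self-reported adherence. It changes who collects data and in what order, and leaves clinical care untouched.
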